Evaluating endothelial dysfunction by assessing coronary vascular function can thus not only index the adverse impact of multiple risk factors but also provide the opportunity to evaluate the benefit of an intervention which targets coronary vascular dysfunction. The synthesis and release of nitric oxide (NO) is an essential component of normal endothelial function. NO’s downstream effects include not only vasodilation and a resultant increase in coronary flow, but also anti-proliferative, anti-coagulant, anti-adhesive, and anti-inflammatory effects⁵. Its beneficial vascular effects are mediated by stimulation of the soluble guanylyl cyclase (sGC) enzyme, which converts guanosine-5'-triphosphate (GTP) to the second messenger guanosine monophosphate (cGMP). cGMP activates GMP-dependent protein kinases (PKG) which in turn phosphorylate several proteins that have vasorelaxant and anti-atherosclerotic effects⁶. Reduced bioavailability of NO associated with endothelial dysfunction, therefore, leads to loss of its important downstream effects, and therefore may be one of the important mechanisms responsible for progression of atherosclerosis and its associated adverse clinical outcomes⁷.

Date: June 3, 2025

Principal Investigator: [name]., PhD.

Application Number: IRB00310207

Hypothesis: Vericiguat improves coronary vascular endothelial function in patients with metabolic syndrome or type 2 diabetes mellitus and impaired coronary vascular function.

We will perform a placebo-controlled, randomized, double-blind study to test the hypothesis, that the administration of vericiguat, which increases soluble guanylate cyclase (sGC) activity despite low NO, improves coronary vascular function in patients with the metabolic syndrome or type 2 diabetes mellitus and coronary vascular dysfunction. We will be using MRI studies to evaluate coronary vascular function in response to study drug administration.

2. Objectives

(include all primary and secondary objectives)

Primary Objective:

1. To characterize the impact of vericiguat on global (micro- and macro- vascular function) coronary vascular function by comparing the responses prior to, and following, vericiguat administration, to isometric handgrip exercise, an endothelial-specific stressor in patients with the metabolic syndrome or type 2 diabetes mellitus and baseline coronary vascular dysfunction.

Secondary Objective:

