1. To compare changes in resting, pre-isometric hand exercise (IHE), coronary blood flow before and following study drug administration within and between the vericiguat and placebo groups.
2. To compare coronary flow and cross-sectional area prior to the isometric handgrip exercise before, and following study drug administration within and between the vericiguat and placebo groups.
3. To obtain serum, plasma, and urine laboratory studies to characterize markers/mediators of inflammation and of the nitric oxide signaling pathway prior to and following up-titration of the study drug.

3. Background

(briefly describe pre-clinical and clinical data, current experience with procedures, drug or device, and any other relevant information to justify the research)

Coronary vascular function can be assessed by examining changes in coronary blood flow and dimension following initiation of a coronary endothelial-dependent stimulus. If function is normal, the stimulus results in a significant increase in coronary blood flow and dimension, but if abnormal, the result is only a small, or no, increase, or even a decrease. These changes were previously assessed via placement of a catheter within the studied artery⁸. Because that procedure is invasive, the associated risks did not justify most studies in individuals without known or suspected significant stenoses or in the serial studies required to assess the benefit of an intervention designed to improve coronary vascular function. The Hopkins investigator team for this proposed study, however, has extensive experience in using MRI methodology to non-invasively and safely study coronary vascular function in healthy individuals⁹ and in those with pro-inflammatory states¹⁰ and coronary disease¹¹ and to perform serial studies to assess the impact of interventions¹².

Date: June 3, 2025

Principal Investigator: [name]., PhD.

Application Number: IRB00310207

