Vericiguat stimulates sGC both independently of, and synergistically with, NO¹⁵. Vericiguat enhances the cGMP pathways by directly stimulating sGC through a binding site independent of NO, and it sensitizes sGC to any bioavailable NO by stabilizing NO binding to the sGC binding site¹⁵. Thus, the beneficial attributes of NO bioavailability may accrue despite the decreased bioavailability associated with the metabolic syndrome. Our study will test whether the coronary vascular response to isometric handgrip exercise (IHE), an endothelial-dependent stressor, improves from the study performed prior to and that performed following the administration of vericiguat. We will also test whether the response differs from the response in those randomized to placebo and whether the results on the follow-up exams differ between those randomized to vericiguat and those randomized to placebo.

If successful, a sGC mediated prevention strategy could be tested to learn whether improved coronary vascular function would improve outcomes in those with, and at risk for, the development and progression of coronary vascular disease (Figure 1).

[figure not shown]

Figure 1: Hypothesis: Vericiguat improves coronary vascular endothelial function in patients with the metabolic syndrome or type 2 diabetes mellitus and impaired coronary vascular function. L-Arg= L-arginine, NO= nitric oxide, eNOS= endothelial nitric oxide synthase, sGC= soluble guanylyl cyclase, cGMP= cyclic guanosine monophosphate, PKG= cyclic GMP-dependent protein kinases

We have extensive experience using magnetic resonance imaging (MRI) to assess coronary endothelial-dependent vascular function non-invasively in healthy individuals and in those with coronary disease¹¹ and pro-inflammatory states¹⁰ using isometric handgrip exercise, an endothelial NO pathway-specific stressor⁹

Our MRI technique can detect meaningful changes in coronary vascular function in people with impaired baseline coronary vascular function following an intervention and we will use this methodology in the proposed study to assess the impact of stimulating sGC with vericiguat on coronary vascular function in patients with impaired baseline function.

4. Study Procedures

a. *Study design, including the sequence and timing of study procedures (distinguish research procedures from those that are part of routine care).*

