b. *Justification and safety information if FDA approved drugs will be administered for non-FDA approved indications or if doses or routes of administration or participant populations are changed.*

Vericiguat is approved for reducing the risk of cardiovascular death and heart failure hospitalization following hospitalization or need for outpatient intravenous diuretics in adults with symptomatic chronic heart failure and ejection fraction less than 45%. The dose and route of administration are the same as that administered for this FDA approved indication. The dose is not changed from that used for the marketed drug.

c. *Justification and safety information if non-FDA approved drugs without an IND will be administered.*

We will be using an FDA approved drug.

7. Study Statistics

a. *Primary outcome variable.*

In a paired analysis, we hypothesize that there is a significant change in coronary flow and dimension with isometric handgrip exercise (IHE) in the group randomized to vericiguat from that measured at baseline, prior to the initiation of vericiguat, to that measured following vericiguat administration and up-titration. We will be using either a paired student t-test or a Wilcoxon test to examine this hypothesis.

In unpaired analyses, we hypothesize that the change in the vericiguat group from baseline to post-up titration will be greater than the change in the placebo group. We will be using either an unpaired student t-test or a Mann-Whitney test to examine this hypothesis

b. *Secondary outcome variables.*

We will conduct bivariate analyses to compare markers/mediators of inflammation and that of the nitric oxide pathway.

Other exploratory outcome variable that we are interested in include age, sex, and race. We will be using parametric and non-parametric tests for continuous variables and chi-square or Fisher's exact tests for categorical variables.

c. *Statistical plan including sample size justification and interim data analysis.*

Date: June 3, 2025

Principal Investigator: [name]., PhD.

Application Number: IRB00310207

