All sample size calculations are based on 80% power and 5% alpha error for two-sided tests. We have prior studies with small sample sizes to inform our baseline expectations¹². For our primary analysis, our minimum expected difference in change in coronary flow with IHE in the vericiguat group with our planned sample size of n=30 in the vericiguat group, allowing for 10% loss to follow-up at 8 weeks (n=27 remaining), with 80% power and an alpha of 0.05 is $7.8\% \pm 13.6\%$. The detectable effect size at 90% power is $9.1\% \pm 13.6\%$. (Figure 3).

[figure not shown]

Figure 3: Power and sample size calculated for estimated difference in change in coronary flow with IHE from baseline to 8 weeks in the vericiguat group

The study investigators will be responsible for analyzing the study data to assess the completeness of data collection, to assess any adverse events, and to identify any findings which may have clinical relevance. This will be performed while maintaining the blind. A Data Safety and Monitoring Committee will review and, if necessary unblind, the data when the outcomes of the first third (n=15) of the anticipated enrolled participants are available and at the end of the study. This committee may request to review/audit the data at any time.

The data will be maintained in a REDCap database.

The data will be unblinded following the completion of the protocol, and medical/scientific review has been completed, protocol violators have been identified and data has been declared complete, although the Hopkins Institutional Review Board and Data Safety and Monitoring Committee may request prior unblinding.

Date: June 3, 2025

Principal Investigator: [name]., PhD.

Application Number: IRB00310207

The routine safety laboratory studies will be analyzed within 48 hours of collection.
The MRI data will be analyzed within two months of each study

d. Early stopping rules.

The study will be stopped early on the recommendation of the Data Safety and Monitoring Committee or if there is any new published information regarding the safety of the study drug or the study procedures.

8. Risks

a. Medical risks, listing all procedures, their major and minor risks and expected frequency.

Study Drug:

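### Section 7a sets no success rule among its primary tests, and the one the plan leads with and powers, paired flow within vericiguat, can turn positive through regression to the mean

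*Combined protocol and SAP*

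**What the plan says.** Section 7a (Primary outcome variable) holds two hypotheses.

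- A paired one within the vericiguat arm: "we hypothesize that there is a significant change in coronary flow and dimension with isometric handgrip exercise (IHE".
- An unpaired one: "we hypothesize that the change in the vericiguat group from baseline to post-up titration will be greater than the change in the placebo group". It does not say whether this means flow, dimension or both.

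No sentence says whether one or both variables must succeed, which test comes first, or how the 5% is shared.

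Section 7c opens with "All sample size calculations are based on 80% power and 5% alpha error for two-sided tests", but its one calculation begins "For our primary analysis, our minimum expected difference in change in coronary flow with IHE in the vericiguat group" and uses 27 patients, a difference of 7.8 and an SD of 13.6. The caption of Figure 3 has the same scope.

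Two other places lean the same way. The primary objective is to be met "by comparing the responses prior to, and following, vericiguat administration", and the Background adds the comparison with placebo second: "We will also test whether the response differs from the response in those randomized to placebo".

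Nothing labels the handgrip-induced change in dimension, or the placebo comparison of the handgrip response, as secondary. Section 7b says "We will conduct bivariate analyses to compare markers/mediators of inflammation and that of the nitric oxide pathway" and then names age, sex and race as exploratory. The secondary objectives concern resting measurements ("To compare coronary flow and cross-sectional area prior to the isometric handgrip exercise before, and following study drug administration") and laboratory markers.

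Section 5 requires a handgrip-induced flow change of at most 13% for entry. In section 4a, patients with an abnormal scan go on to echocardiography, laboratory tests and randomisation. The MRI methods provide a second screening scan only for technical problems.

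**The concern.** The plan does not say which result would make the trial positive. If the reader follows the hints and takes paired flow within vericiguat as the lead, a randomised, placebo-controlled trial is judged on a before-after comparison in one arm.

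That comparison has a specific weakness here. Patients are admitted because a measured value of the same variable was low, and as far as the text shows, that measurement is also the baseline. Some of them were low on the day by chance and will read higher at the final MRI with no drug effect. The placebo comparison is protected because both arms are selected in the same way before randomisation. It is the comparison for which section 7c gives no power.

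**Working it through.** **1. What the stated power covers.** Inputs from section 7c: 30 × 0.9 = 27 patients, difference 7.8, SD 13.6, two-sided 5%. In a paired t-test the standard error is 13.6/√27 = 2.617. The noncentrality is 7.8/2.617 = 2.980 on 26 df (critical t 2.056), which gives power of 81.8%. For 9.1 it is 3.477, giving 91.7%. The plan's figures therefore reproduce as a within-arm test, with 13.6 read as the SD of the paired change.

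**2. The same effect against placebo.** Section 4a gives 15 placebo patients, and 15 × 0.9 = 13.5, taken as 13. Assume SD 13.6 in both arms and no placebo change. The standard error is 13.6 × √(1/27 + 1/13) = 13.6 × 0.3376 = 4.591. The noncentrality is 7.8/4.591 = 1.699 on 38 df (critical t 2.024), which gives power of 38.1%. The difference detectable at 80% power is 13.2 points. Varying one assumption at a time:

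- SD 10 to 16: power 61% to 29%, detectable difference 9.7 to 15.5 points.
- 12 to 15 placebo patients: power 36% to 41%.
- Placebo change of −2 or +2 points: power 55% or 23%.

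**3. Regression to the mean with no drug effect.** Model: screening value = true value + error, kept if 13 or less and used as baseline; final value = same true value + new error. The documents give no unselected mean m, between-patient SD b or scan-to-scan SD e, so all three are assumed: m 0 to 10, b 5 to 10, e 5 to 9.6. The upper e is 13.6/√2, which treats all of the 13.6 as scan-to-scan error.

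With s² = b² + e² and k = (13 − m)/s, the expected rise is (e²/s) × φ(k)/Φ(k).

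- Low end (m = 0, b = 5, e = 5): s = 7.07, k = 1.84, rise = 3.536 × 0.0761 = 0.27 points.
- High end (m = 10, b = 5, e = 9.6): s = 10.82, k = 0.277, rise = 8.51 × 0.630 = 5.37 points.

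Simulated trials, 27 versus 13, 40,000 per setting:

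| Scan-to-scan SD | Paired flow falsely favourable | Nominal |
|---|---|---|
| 5 | 4% to 31% | 2.5% |
| 7 | 6% to 46% | 2.5% |
| 9.6 | 11% to 62% | 2.5% |

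In every setting the placebo comparison rejected in 4.9% to 5.2% of trials, two-sided.

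**4. Several tests, no rule (illustrative).** With no true change and no selection effect, two-sided error is about 9% if either flow test, paired or against placebo, could carry the claim. If any of four tests could (flow and dimension, paired and against placebo), it is 16.5% to 12.3% for an assumed flow-dimension correlation of 0.3 to 0.9. If both paired variables must succeed, error falls to 0.5% to 2.9%. Power is then 69% to 77% if dimension has the same standardised effect as flow (7.8/13.6 = 0.57 SD).

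**The case against.** The strongest reply is that the lead test can be identified. Section 7c speaks of a primary analysis and describes paired flow, the primary objective is before versus after vericiguat, and the Background adds placebo second. On that view section 7a merely fails to label the rest as supporting, and one sentence would close the gap. The placebo arm is already there as a check, and this is a 45-patient mechanistic study. Much of this stands: a reader might infer that the plan has no discernible lead, and the documents do not support that. But labelling paired flow as the sole primary would settle the rule by resting the claim on the one test that selection can bias.

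A reader might also infer that the trial runs a 12% to 16% false-positive risk. The documents do not support that either. It needs any of four tests to suffice, whereas section 7a joins flow and dimension with *and*, and the unpaired test names no variable, so the count of four is itself an assumption.

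On selection, the MRI analysis section reports low observer variability and good reproducibility over eight weeks, without a figure. That supports the lower end of the range. The upper end leaves no room for patients to differ in their response to the drug. Figure 2, the study overview, is not shown, so the absence of a fresh baseline scan is established for the text only.

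**Conclusion.** The point holds in this form. Section 7a lists several tests as primary with no success rule. The plan leans towards paired flow within vericiguat, and its 80% and 90% power belong to that test only. Because entry depends on a low measured value of the same variable, that test can be positive without a drug effect.

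The direction of the bias is secure; its size is not. A rise of 0.3 to 5.4 points and a false favourable rate of 4% to 62% depend wholly on the assumed mean and SDs. A reader might infer that a positive paired result would be mostly artefact, but the documents do not show that: at the lower end the rate is close to nominal. The placebo comparison avoids the problem, at about 38% power for 7.8 points under the assumptions in step 2. The multiplicity figures are illustrations of what an unstated rule permits, not the trial's error rate.

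**What to change.** **Section 7a.**

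- Make the primary test the vericiguat-versus-placebo difference in change, from baseline to the final MRI, in handgrip-induced % change in coronary blood flow, at two-sided 5%.
- Test handgrip-induced change in cross-sectional area versus placebo next, at two-sided 5%, only if the first test is significant.
- Report the paired analyses within vericiguat as supportive and descriptive, not as a gate to any other test. State that they cannot separate a drug effect from regression to the mean.

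**Primary objective.** Reword it to match this comparison.

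**Section 7c.** Label the 80% and 90% figures as applying to the paired within-arm test only. Add the power of the primary comparison: about 38% at 7.8 points, or about 13 points detectable at 80% power. State the assumptions (27 versus 13 analysed, SD of change 13.6 in both arms, no placebo change) and the range of 61% to 29% for SD 10 to 16.

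**Cost.** A few sentences, with no new patients, visits or data. The stated power becomes less favourable, which the sponsor must accept or address openly. The within-arm result no longer leads, and dimension cannot carry a primary claim by itself. The low power against placebo is already in the design; the change only makes it visible.

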For men >40 and women >50 years of age who have not had coronary angiography (including CT angiography) within the prior 36 months, a CAC score will be determined. A computed tomography (CT) scan will be performed without contrast agents with 10 to 15 minutes of total room time at about 1 to 2.5 mSv of radiation²².

MRI methods for Coronary Vasoreactivity:

MR will be performed on a 3 T CMR scanner (Achieva, Philips Healthcare, Best, NL) in the morning after an overnight fast. For endothelial function imaging, alternating anatomical and velocity-encoded images will be collected at baseline and during approximately 6 min of continuous isometric handgrip exercise (IHE). The exercise is performed using a handgrip dynamometer at 30% of each participant's maximum force, which is determined prior to the MRI study, as previously reported^{9,23}. Images will be taken perpendicular to a proximal or mid-straight segment of the coronary artery and/or coronary sinus best identified on survey scans¹¹. Cross-sectional anatomical (bright blood sequence) and phase contrast velocity encoded spiral CMR will be obtained using single breath-hold cine sequences with reproducibility of the techniques published previously^{9,23}. The MRI will be used to measure cross-sectional area (CSA), coronary flow velocity (CFV), and to calculate coronary blood flow (CBF) changes in response to the IHE. If technical problems prevent adequate interrogation of the coronary response, the participant will be asked to undergo a second screening MRI study. Coronary MRI will be repeated following the study drug administration period with an identical protocol with special attention taken to interrogate the same coronary segments as those studied at baseline, using anatomic landmarks of coronary ostia and branch vessels- as we have done in the past⁹ and to replicate the identical MRI IHE protocol.

MRI analysis:

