Images will be analyzed blinded to study-drug assignment and clinical information for CEF (e.g., change in cross-sectional area (CSA), coronary flow velocity (CFV), and calculated coronary blood flow (CBF), as previously validated and described^{9,23}. Coronary CSA will be quantified using a semi-automated software tool (Cine version 3.15.17, General Electric, Milwaukee, WI, USA) as previously reported¹¹. For CBV and CBF measurements, phase-contrast images will be analyzed using semi-automated commercial software (FLOW Version 3.0, Medis, NL); the coronary blood-flow (CBF, in ml/minute) is derived from diastolic coronary flow velocity (CFV, in cm/sec) as previously described^{9,11}. Only native coronary segments will be analyzed. Our prior studies using this methodology demonstrated low intra- and inter-observer variability with good reproducibility over eight weeks⁹.

Echocardiography

Participants may also be asked to undergo echocardiographic studies to evaluate cardiac function. Systolic function will be assessed by measuring the ejection fraction (EF), calculated as stroke volume divided by the end-diastolic volume. Diastolic function will be assessed by looking at the annular e' velocity, the septal and lateral e' velocities, the average E/e' ratio, the LA volume index and the peak TR velocity²⁴. We will obtain images before and after a 90 second passive leg raise as well to assess hemodynamic variations²⁵. Strain and strain rate measurements will be obtained

using myocardial speckle tracking to evaluate regional myocardial contractile function²⁶.

b. *If your study involves data/biospecimens from participants enrolled under other research studies with a written consent or under a waiver of consent, please list the IRB application numbers for those studies. Please note: Certificate of Confidentiality (CoC) protections applied to the data in source studies funded by NIH or CDC will extend to this new study if the funding was active in 2016. If this situation applies, Section 36, question 6 in the application will need to be answered "Yes" and "Hopkins Faculty" should be selected in question 7. No other documents are required.*

Not applicable

c. *Study duration and number of study visits required of research participants.*

Study Duration: 24 months

Number of study visits per participant: 4 to 8, depending on whether the MRI and echo will be performed on the same day and how many titration steps are performed.

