 - fasting high-density lipoprotein (HDL) cholesterol level < 40 mg/dL in men or < 50 mg/dL in women
 - fasting blood glucose > 100 mg/dL or HbA1c $\geq 5.7\%$
- Either one of the following:
 - Men ≤ 40 or women ≤ 50 years of age with no history or symptoms of ischemic heart disease, or
 - Men >40 or women >50 years of age with either one of the following:
 - a coronary angiography (including CT angiography) within the past 36 months showing no significant coronary artery disease in at least one major coronary artery, defined as $>50\%$ stenosis of the left main coronary artery and/or $>70\%$ stenosis of another major coronary vessel, or
 - a coronary artery calcium score obtained within the prior 36 months or if no prior calcium scan, one performed as a research study following consent with a score ≤ 10 in at least one major coronary artery.
- IHE-induced %-change in coronary flow < or equal to 13%

Exclusion Criteria:

- Systolic blood pressure <110 mm Hg
- Current or anticipated use of long-acting nitrates, a sGC stimulator, or phosphodiesterase type 5 (PDE5) inhibitors
- Hematocrit $<30\%$
- Unable to understand the risks, benefits, and alternatives of participation so as to provide informed consent
- Women who are pregnant.
- Women who are breastfeeding
- Women with reproductive capacity not using an acceptable form of contraception
- History of claustrophobia
- Inability to lie flat and still for 45 minutes

- Presence of non-MR-compatible objects or devices, such as intra-orbital debris, intra-auricular implants, intra-cranial clips, an implanted defibrillator or a pacemaker
- History as a machinist, welder, metal worker or a similar activity that poses the risk of metal exposure to the eyes

6. Drugs/ Substances/ Devices

a. *The rationale for choosing the drug and dose or for choosing the device to be used.*

As detailed above, we propose using vericiguat to “bypass” the requirement for nitric oxide synthesis in an attempt to improve endothelial function and hence coronary vascular function in individuals with preexisting dysfunction²⁷. If successful, a sGC-directed prevention strategy may improve coronary vascular function and decrease cardiovascular risk. The dose and titration described to reach the dose is that used for patients with heart failure and approved by the FDA to treat those patients²⁸.

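### Section 7a's between-arm test on change scores fixes the baseline slope at 1; ANCOVA would estimate it at almost no cost, for a gain that the documents cannot size and that may be nil

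*Combined protocol and SAP*

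**What the plan says.** Section 7a (Primary outcome variable) has a paired hypothesis within the vericiguat arm and an unpaired one between arms. The unpaired hypothesis is that "the change in the vericiguat group from baseline to post-up titration will be greater than the change in the placebo group". The method is: "We will be using either an unpaired student t-test or a Mann-Whitney test to examine this hypothesis". No section names a baseline covariate or an adjusted model. Section 3 (Background) also mentions comparing follow-up results alone between arms.

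Three other places bear on the baseline value:

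- **Section 5** requires "IHE-induced %-change in coronary flow < or equal to 13" per cent, so the baseline response that enters the change score also decides entry.
- **Section 4a (MRI methods)** plans one baseline scan, with a second screening scan only after technical problems. Then: "Coronary MRI will be repeated following the study drug administration period with an identical protocol".
- **Section 4a (MRI analysis)** cites "low intra- and inter-observer variability with good reproducibility over eight weeks" from earlier studies, with no correlation or SD.

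Section 7c sizes only the within-arm test: "For our primary analysis, our minimum expected difference in change in coronary flow with IHE in the vericiguat group". It gives 7.8 ± 13.6 points at 80% power with 27 of 30 participants remaining.

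**The concern.** A test on follow-up minus baseline is an adjusted comparison with the baseline coefficient set to 1. A follow-up-only test sets it to 0. The plan has both and estimates neither. Measurement error in a single baseline scan pulls the true follow-up-on-baseline slope below 1. A coefficient of 1 then over-corrects and leaves baseline noise in the contrast.

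This comparison is the one that uses the randomization, and it is small and unsized. Precision available from data already collected would be worth having. What is at stake is the width of the between-arm confidence interval, not its validity.

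**Working it through.** **Inputs from the documents:** SD 13.6, differences 7.8 and 9.1, two-sided 5% alpha, 27 vericiguat completers (7c); arms of 30 and 15 (4a); entry cut of 13% (5). **Assumed:** 10% loss in placebo as well (15 × 0.9 = 13.5, taken as 13), the same SD in both arms, normal errors. Baseline mean and reliability are not in the documents and are varied.

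**1. The plan's own figure.** Paired t-test, n = 27: SE = 13.6/√27 = 2.617. For 7.8 the noncentrality is 2.98, against a critical t of 2.056, and power is 81.8%. For 9.1 power is 91.7%. Both agree with 7c within 2 points.

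**2. The between-arm change-score test.** SE = 13.6 × √(1/27 + 1/13) = 4.591 and 7.8/4.591 = 1.699. The critical t on 38 df is 2.024. Power is 38.1% and the 95% CI half-width is 2.024 × 4.591 = 9.3 points. With 14 placebo completers power is 39.7%.

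**3. Cost of estimating the slope.** The variance factor is 1 + 1/(40 − 4) = 37/36 = 1.028, and critical t moves from 2.024 to 2.026. If the true slope is exactly 1, power falls from 38.1% to 37.2%.

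**4. Gain if all of the 13.6 is measurement error.** Split equally between the scans, the error SD is 13.6/√2 = 9.6 per scan. Let r be the reliability before selection, which equals the within-arm slope under this model. Let v be the baseline variance after the 13% cut divided by that before it. Then

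ratio (ANCOVA/change score) = (1 − r²) / [(1 − r²) + (1 − r)²v] × 37/36.

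Example: r = 0.59 and baseline mean 13 give v = 0.363. The ratio is 0.652/(0.652 + 0.168 × 0.363) × 1.028 = 0.94.

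| r (baseline SD) | mean 0 | mean 13 | mean 20 |
|---|---|---|---|
| 0.24 (11) | 0.725 | 0.841 | 0.892 |
| 0.59 (15) | 0.892 | 0.940 | 0.960 |
| 0.77 (20) | 0.962 | 0.981 | 0.990 |
| 0.90 (30) | 1.003 | 1.008 | 1.011 |

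Simulation agrees to about 0.01: 0.73-0.88, 0.89-0.96, 0.96-0.99 and 1.00-1.02 for the four rows. Setting the ratio to 1 gives r = (36v − 1)/(36v + 1), a break-even of 0.89, 0.86 and 0.83 at means 0, 13 and 20.

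Simulated power at mean 13, change score to ANCOVA, is 47.9% to 54.7% (r = 0.24), 42.9% to 45.1% (0.59), 40.8% to 41.4% (0.77) and 39.0% to 38.6% (0.90). These start above 38.1% because the simulation takes 13.6 as the SD before the entry cut, which then shrinks it. If 13.6 is the SD among those enrolled, the ratios are 0.73-1.01 and power goes from 37-39% to 37-49%.

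**5. Gain if a share s of the 13.6² is real variation in change.** This part adds to follow-up only. With baseline SD B, the error variance per scan is e² = 13.6²(1 − s)/2, the slope is r = 1 − e²/B², and the residual variance is R = B²(1 − r²) + s × 13.6². The ratio is R/[R + (1 − r)²B²v] × 37/36. The shares below are assumptions.

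| s, B | mean 0 | mean 13 | mean 20 |
|---|---|---|---|
| 25%, 15 | 0.954 | 0.981 | 0.992 |
| 25%, 20 | 0.991 | 1.002 | 1.007 |
| 50%, 15 | 0.996 | 1.008 | 1.013 |
| 50%, 20 | 1.012 | 1.017 | 1.019 |

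Simulation gives about 0.96-1.02 over this range.

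**6. Effect varying with baseline** (simulated, mean 13, all measurement error). If the effect rises 0.3 per baseline point, the ratio is 1.025 at r = 0.77 and 1.041 at 0.85. If it falls 0.3 per point, the ratio is 0.952 and 0.967.

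**7. Type I error.** Simulated at zero difference, it is 0.048-0.051 for the change-score t-test, Mann-Whitney and ANCOVA.

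**The case against.** The strongest reply is that nothing here is an error. The change-score test already uses baseline, is unbiased under randomization and holds its alpha. That stands: this is a suggestion about efficiency.

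A second reply is that the documents do not establish any gain. Their only evidence, good reproducibility over eight weeks, points to the end where the ratio is close to 1. Treating the whole 13.6 as measurement error is itself an assumption that favours ANCOVA, since 7c attaches that SD to a change under treatment, which may include real differences in response. This also stands. It is why the gain may be nil, and why the 0.83-0.89 break-even holds only under the all-measurement-error assumption.

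Third, Mann-Whitney on change can beat ANCOVA. With lognormal-shaped follow-up error (mean 13) its power is 51.0% vs 49.6% at r = 0.59, 47.5% vs 45.1% at 0.77 and 45.7% vs 42.9% at 0.85; at 0.24 ANCOVA leads, 61.3% vs 60.2%. With normal errors Mann-Whitney is 2-3 points below the change-score t-test. The documents do not give the error distribution, so Mann-Whitney should stay in the plan.

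Finally, 7c calls the within-vericiguat change its primary analysis, and ANCOVA leaves that untouched. That limits the priority of the edit. It does not remove the case for it, because the between-arm test is also listed under the primary outcome.

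**Conclusion.** The point holds as a low-priority, nearly costless improvement. The planned test fixes the slope at 1, and the plan nowhere estimates it. ANCOVA loses at most about 3% of variance with a constant effect, and about 4% in the least favourable varying-effect case tried. Its benefit ranges from material at low reliability to none or slightly negative at high reliability, or where much of the SD of change is real variation. The documents do not say which case applies, and none of these ranges is a bound.

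Three stronger readings are not supported:

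- A reader might infer that selecting on a low baseline biases the between-arm comparison through regression to the mean. Both randomized arms are selected alike, so it affects them equally.
- A reader might infer that ANCOVA would make the comparison adequately powered. Starting from about 38%, it would not do so in any scenario tried.
- A reader might carry the flow results over to coronary dimension. The gain for cross-sectional area was not quantified, and the 13% cut applies to flow only.

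All of this assumes 27 vs 13 completers, a common SD and, except where stated, normal errors and a constant effect.

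**What to change.** In Section 7a, prespecify the between-arm analysis as an ANCOVA: follow-up IHE-induced % change in coronary flow on treatment arm, with the baseline IHE-induced % change as covariate. Report the adjusted difference with its 95% CI. Fit the same model for cross-sectional area with its own baseline value. Keep the Mann-Whitney test on change scores as a prespecified sensitivity analysis. The follow-up-only comparison in Section 3 can be answered by the same model, or labelled supportive if kept as a separate test.

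The cost is one or two sentences, one degree of freedom per model, the small variance loss given above, and no new data. Naming one main model also settles the open choice between two tests for this comparison. The missing sample-size basis for the between-arm test is a separate matter that this edit does not address.
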